#### ***Neutrophils***

The incidence of neutropenia by maximal grade (lowest neutrophils value reported) during the TEAE period will be summarized. The 4 grades are defined as below:

- Grade 1:  $\geq 1.5$  Giga/L-LLN
- Grade 2:  $\geq 1.0$  Giga/L-1.5 Giga/L
- Grade 3:  $\geq 0.5$  Giga/L-1.0 Giga/L
- Grade 4: <0.5 Giga/L

For patients with Grade 3 or 4 neutropenia, a listing with the individual neutropenia counts, WBC, platelet counts, lymphocytes and hemoglobin at each visit (including unscheduled visits for re-test) will be provided. In addition, the neutropenia counts at each scheduled visit during the study will be plotted by previous treatment prior to enrollment into LTS11210. In addition, summaries will include the following data: discontinuation, restart dosing, dosing delay, number of episodes, and normalization (to >LLN or return to baseline if baseline is <LLN). The labs measured during the post-study period will be considered in the analysis of normalization.

Summaries of neutropenia by maximal grade at dose regimens (150 mg qw, 150 mg q2w, 200 mg q2w) may be provided.

### ***Liver function tests***

The liver function tests, namely AST, ALT, alkaline phosphatase and total bilirubin are used to assess possible drug induced liver toxicity. The proportion of patients with PCSA values at any post-baseline visit by baseline status will be displayed by treatment group for each parameter. The proportion of patients with PCSA values at any post baseline visit may be displayed by duration of exposure for each treatment group.

A graph of distribution of peak values of ALT versus peak values of total bilirubin will also be presented. Note that the ALT and Total bilirubin values are presented on a logarithmic scale. The graph will be divided into 4 quadrants with a vertical line corresponding to 3xULN for ALT and a horizontal line corresponding to 2xULN for total bilirubin.

The normalization (to  $\leq 1$  ULN) or return to baseline (in case of baseline is >ULN) of elevated liver function tests will be summarized by categories of elevation (>3 ULN, >5 ULN, >10 ULN, >20 ULN for ALT and AST; >1.5 ULN for ALP; and >1.5 ULN and >2 ULN for total bilirubin), with following categories of normalization: 1) normalized on-treatment; 2) normalized after last dose; 3) last value not normal. The laboratory values measured during the post-study period will be considered in the analysis of normalization. Note that a patient will be counted only under the maximum elevation category.

#### **2.4.4.4 Analyses of vital sign variables**

The summary statistics (including number, mean, median, standard deviation, minimum and maximum) of all vital signs variables (vital signs values and changes from baseline) will be calculated for each visit or study assessment (baseline, each post baseline time point, and endpoint) by treatment group.

The incidence of PCSAs at any time during the TEAE period will be summarized by treatment group whatever the baseline level and/or according to the following baseline status categories:

- Normal/Missing
- Abnormal according to PCSA criterion or criteria

Listings will be provided with flags indicating the PCSA values.

#### **2.4.4.5 Analyses of ECG variables**

The summary statistics (including number, mean, median, standard deviation, minimum and maximum) of all ECG variables (ECG values and changes from baseline) will be calculated for each visit or study assessment (baseline, each post baseline time point, and endpoint) by treatment group.

The incidence of PCSAs at any time during the TEAE period will be summarized by treatment received whatever the baseline level and/or according to the following baseline status categories:

- Normal/Missing
- Abnormal according to PCSA criterion or criteria

Listings will be provided with flags indicating the PCSA values.

#### **2.4.5 Analyses of efficacy endpoints**

There will be no confirmatory analysis for the efficacy variables. All analysis will be done descriptively on the safety population by visit in observed case, as appropriate. In addition to the by-visit analysis, efficacy assessments summarized on a yearly basis will be provided.

The baseline value for efficacy parameters is the original baseline from the previous studies. The value at Week 0 is the last non-missing measurement in data collected at scheduled visits: visit1, visit2, and/or visit1/2 in LTS11210 or EOT visit of previous studies prior to first IMP in LTS11210 study.

For categorical variables, for example, percentage of patients who have maintained/reached ACR20 overtime, the number and percentage will be provided from all patients who have data available at that time point, and the 95% confidence intervals (CI) will be calculated if appropriate.

For continuous variables, descriptive statistics such as the mean, standard deviation, median, minimum and maximum will be provided. In addition, 95% confidence interval of the mean will be presented. This applies to the original values and change (or percent change) from baseline.

The 2-year (EFC11072 52 weeks + LTS11210 48 weeks) X-ray data from Campaign 1 will be described using the van der Heijde modified total Sharp score for the subset of patients who previously completed study EFC11072, Part B when the 2-year X-ray data are available for all these patients. The modified total Sharp score and the change from baseline in the modified total sharp score will be described using mean, standard deviation, median, minimum and maximum, along with 95% confidence intervals. There is no formal treatment comparison and no alpha adjustment will be made (further analyses will be in the report of integrated summary of efficacy). In addition, the incidence of radiographic progression will be summarized using descriptive statistics.

The above analyses will also be performed for X-ray data from Campaign 2 and Campaign 3 respectively once X-ray data are available.

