##### 9.1.2.1 ACR20/ACR50/ACR70

Signs and symptoms are assessed with a composite rating scale of the ACR (American College of Rheumatology) that includes 7 variables:

- Tender Joints Count (TJC)
- Swollen Joints Count (SJC)
- Levels of an acute phase reactant (CRP level)
- Patient's assessment of pain
- Patient's global assessment of disease activity
- Physician's global assessment of disease activity
- Patient's assessment of physical function

The details of the ACR score are presented in [Appendix B](#).

ACR20 is defined as the percentage of patients who achieve at least 20% improvement in both tender joint count and swollen joint count and, at least 20% improvement in at least 3 of the 5 other assessments.

ACR50 is defined as the percentage of patients who achieve at least 50% improvement in both tender joint count and swollen joint count and, at least 50% improvement in at least 3 of the 5 other assessments.

ACR70 is defined as the percentage of patients who achieve at least 70% improvement in both tender joint count and swollen joint count and, at least 70% improvement in at least 3 of the 5 other assessments.

ACR scores will only be assessed up to Week 264 at the time points as per study flowchart.

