## 12 STUDY PROCEDURES

### 12.1 VISIT SCHEDULE

It is preferred that all study visits take place in the morning. Some visits that include only scheduled blood sampling (V3, V5, V6.1) (Week 2, Week 6, and Week 10) can be scheduled as Home Visits or clinic visits.

Patients will be considered as having completed their treatment per protocol and should complete the end of treatment visit (EOT):

- At Week 264, if sarilumab has been commercialized in their country at that time. EOT visit should be performed instead of Week 264 visit and the assessments defined in the flowchart ([Section 1.2.1](#), [Section 1.2.2](#)) should be completed.
- At any visit after Week 264 once sarilumab is commercialized in their country (applicable for patients in the countries where commercial sarilumab is not available at the time the patients completed their Week 264). Some of the assessments are NOT required at EOT for these patients; please refer to the flowchart ([Section 1.2.1](#), [Section 1.2.2](#)) for details.
  - When commercialization occurs in a given country, investigators in that country will be alerted by the Sponsor and they will inform their patients during the next scheduled study visit that their subsequent visit 12 weeks later will be the EOT visit.
- At any visit after Week 264 at the time the study is closed in 2020 in countries where commercialization has still not occurred. Some of the assessments are NOT required at EOT for these patients; please refer to the flowchart ([Section 1.2.1](#), [Section 1.2.2](#)) for details.
  - EOT visits for all patients remaining in the study at that time will occur at scheduled clinic visits over a 3-month period in order to stagger the completion of EOT visits across the study, and allow the completion of the 6-week follow up period for all patients prior to study closure. Investigators will be alerted by the Sponsor that the study closure is approaching and they will inform their patients during the next scheduled study visit that their subsequent visit 12 weeks later will be the EOT visit.
- At Week 264, for patients in the UK no matter when the sarilumab is commercially available in the country. EOT visit should be performed instead of Week 264 visit and assessments defined in the flowchart ([Section 1.2.1](#), [Section 1.2.2](#)) should be completed.

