**12.1.11 Visit 30 (Week 288), Visit 32 (Week 312), Visit 34 (Week 336), Visit 36 (Week 360), Visit 38 (Week 384), Visit 40 (Week 408), Visit 42 (Week 432), Visit 44 (Week 456), Visit 46 (Week 480), Visit 48 (Week 504): On treatment visits from Week 288 to week 504**

This section refers to on-treatment visits with less complex clinical assessments, for patients who are continuing in the study after week 264 because sarilumab is not yet commercialized in their country.

The Investigator will:

- Check compliance to the study drug and concomitant medication and record any changes in the patient's CRF.
- Record vital signs including body temperature, blood pressure, HR and body weight.
- Physical examination will be done only at weeks: 288, 336, 384, 432 and 480.
- Tuberculosis assessment. In case of suspicion of tuberculosis, refer the patient to a TB specialist for complete examination and additional work-up (see specific instructions in [Section 10.2.1](#)).

- Inquire regarding AE/SAEs.
- Obtain (fasting) blood for complete clinical laboratory determinations including:
  - hematology
  - clinical chemistry profile
  - LFTs (no PT required)
  - lipids (only TC, HDL cholesterol, LDL cholesterol, triglycerides) will only be done at weeks: 288, 336, 384, 432 and 480.
- Obtain blood sample for acute phase reactant: hs-CRP.
- Before dosing, obtain serum sample for PK (sarilumab) and for anti-sarilumab antibody.
- Obtain blood sample for ANA at week 288, 336, 384, 432 and 480, or sooner if clinically indicated.
- Obtain urine sample for urine pregnancy test for female of child bearing potential. The patients should be instructed to do the urine pregnancy test at home on a monthly basis during the intervals in between on-treatment clinic visits for the duration of the treatment period. In case of a positive pregnancy test, the patient should be advised to stop the IMP and to contact immediately her study doctor.
- Perform a complete joint examination to assess tender and swollen joints. Only the 28 joints required for DAS28 calculation need to be evaluated (see [Appendix B](#)).
- Ask the patient to complete patient's global assessment.
- Dispense Investigational Product (12-week supply) and remind instructions on self-injection and dosing; and provide self-injection diary.
- The study coordinator or designee will administer the subcutaneous injection (if 14±3 days from last administration) and will observe the patient for 30 minutes.

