### ***Amendment 9***

- Adjust timepoints up to Week 264 for efficacy endpoints (except DAS28 and EULAR) and health economic variables
- The timepoints are up to Week 516 for DAS28 and EULAR endpoints
- Updated analysis treatment groups for patients from EFC11072, ACT11575, EFC10832 and SFY13370 with sarilumab + DMARD therapy in the initial and current studies , and for patients from EFC13752 with sarilumab monotherapy in the initial and current studies, per previous SAP version 2
- Clearly state serum concentrations of bound Sarilumab are not analyzed per sponsor’s decision after EFC11072 study
- Clearly state 3 campaigns of x-ray data (2 year data up to Week 48, 3 year data up to Week 96, and 5 year data up to Week 192 in LTS11210)
- Add the PFS-S sub-study (see Protocol Amendment 9 Appendix R)

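### After Week 264 the by-visit DAS28 and EULAR summaries mix a change in who remains with change within patients, and no planned analysis separates the two

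*SAP*

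**What the plan says.** **How efficacy is summarised.** The general rule in SAP 2.4.5 is "All analysis will be done descriptively on the safety population by visit in observed case, as appropriate". For categorical endpoints the same section adds that "the number and percentage will be provided from all patients who have data available at that time point". SAP 2.5.2 leaves DAS28-CRP missing when any of its four components is missing.

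**How far the series run.** SAP 1.5, under Amendment 9, says: "The timepoints are up to Week 516 for DAS28 and EULAR endpoints". SAP 2.1.4 agrees: DAS28-CRP, DAS28 remission and EULAR response are listed over time without the Week 264 limit placed on ACR and HAQ-DI. Protocol 9.1.2.1 says that "ACR scores will only be assessed up to Week 264 at the time points as per study flowchart".

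**Who is still there.** Protocol 12.1 has patients complete treatment as follows: "At Week 264, if sarilumab has been commercialized in their country at that time". It also has them complete "At Week 264, for patients in the UK no matter when the sarilumab is commercially available in the country". Protocol 12.1.11 describes the Week 288 to Week 504 visits as being "for patients who are continuing in the study after week 264 because sarilumab is not yet commercialized in their country". After a later launch, Protocol 12.1 has patients told at their next scheduled visit, with the end-of-treatment visit 12 weeks after that. Everyone remaining leaves at the 2020 closure. SAP 1.1 notes that some patients may complete at 260 weeks under Amendment 8.

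**What splits are planned.** SAP section 2 presents DMARD combination and monotherapy separately, each by previous treatment and overall. SAP Appendix B enters No for supportive, subgroup and other analyses of DAS28-CRP, DAS28 remission and EULAR response. The country pooling in SAP 2.5.6 uses three geographic regions, not launch status.

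**The concern.** The change of population at Week 264 is scheduled and set by country. It is not ordinary dropout. Patients who complete at Week 264 have their end-of-treatment visit in place of the Week 264 visit, and SAP 2.5.4 maps the 260-week completers to Visit 28, which is Week 264. All of them count in the Week 264 summary and none appears at Week 288.

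A step or drift in the plotted mean or rate after Week 264 could therefore arise although no patient changed. Equally, a real change could be hidden. Long-term efficacy is the secondary objective (Protocol 5.2), and after Week 264 the DAS28-based measures are the only clinical efficacy measures still collected. A reader has nothing else to set against the curve.

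**Working it through.** **Plan's own figure.** Protocol 6.2 gives a maximum participation of 523 weeks: 1 + 516 + 6 = 523. This reproduces. The scheduled DAS28 visits after Week 264 are Weeks 288 to 504 every 24 weeks: (504 − 288)/24 + 1 = 10 visits, plus end of treatment.

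**Selection by enrolment date.** Inputs are the closure in 2020 and the 6-week follow-up that must finish before it (Protocol 12.1). The latest possible first dose for a patient to reach Week w is the closure date minus 6 weeks minus w weeks. The exact closure date is not given, so both ends of 2020 are shown.

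| Week reached | Closure 1 Jan 2020 | Closure 31 Dec 2020 |
|---|---|---|
| 288 | 14 May 2014 | 14 May 2015 |
| 384 | 11 Jul 2012 | 11 Jul 2013 |
| 504 | 24 Mar 2010 | 24 Mar 2011 |
| 516 | 30 Dec 2009 | 30 Dec 2010 |

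The original protocol is dated February 2010 (SAP 1.6). The last points can therefore come only from the earliest enrollees, as Protocol 6.2 itself says.

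**Selection by launch status.** A patient contributes after Week 264 only if sarilumab was not commercially available in the country at that patient's Week 264 and the patient is not in the UK. Visits are 12 weeks apart at this stage, counting dispensing visits. A patient past Week 264 can thus remain for up to about 12 + 12 = 24 weeks after a later launch.

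**Size of the step at the boundary.** Let p be the share continuing past Week 264, and let S and L be the Week 264 values in stayers and leavers.

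- Displayed value at Week 264: pS + (1 − p)L
- Displayed value just after, with no patient changing: S
- Artificial shift: S − [pS + (1 − p)L] = (1 − p)(S − L)

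The documents give neither p nor S − L, so both are assumptions. The table shows the absolute shift in the remission rate, in percentage points.

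| p | gap 0 | gap 5 | gap 10 | gap 15 |
|---|---|---|---|---|
| 0.1 | 0 | 4.5 | 9.0 | 13.5 |
| 0.3 | 0 | 3.5 | 7.0 | 10.5 |
| 0.5 | 0 | 2.5 | 5.0 | 7.5 |
| 0.8 | 0 | 1.0 | 2.0 | 3.0 |

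For mean DAS28-CRP, an assumed gap of 0.2 to 0.6 over the same p gives a shift from 0.8-share continuing, (1 − 0.8) × 0.2 = 0.04, to 0.1-share continuing, (1 − 0.1) × 0.6 = 0.54. A zero gap again gives zero. The sign follows S − L, which is unknown.

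**Fixed cohort.** If only patients assessed after Week 264 are shown on both sides of the boundary, p = 1 and the shift there is (1 − 1)(S − L) = 0.

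**The case against.** The strongest reply has five parts.

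- **The analysis is descriptive, with no confirmatory efficacy test.** This stands. No error rate is at issue, and the point does not concern the primary endpoint, ACR or HAQ-DI.
- **Results are already split.** A reader might infer that the SAP runs a single undivided series across the break. It does not: results are given by previous treatment and by combination versus monotherapy. This partly separates parent-study mix, but each group still contains both leavers and stayers at Week 264.
- **The number of patients with data is shown, and DAS28-CRP and EULAR use change from the original baseline.** Both help. The n reveals that the group has shrunk, but not whether those remaining already differed. Change from baseline removes differences in starting level, but not differences in response.
- **Exit is administrative, not driven by response.** This stands as to direction. The documents give no reason to expect stayers to do better or worse, and a zero difference is possible.
- **Protocol 13.5.5 allows additional sensitivity analyses.** It does, but none is specified for this.

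A reader might also infer that every value after Week 264 comes from a country without commercial sarilumab. That is too absolute, because patients past Week 264 stay for a time after a later launch and their end-of-treatment value is then mapped to a regular visit. The right condition is availability at the patient's own Week 264.

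**Conclusion.** The point holds as a limit on interpretation. Overall and within each planned presentation group, the DAS28-CRP, DAS28 remission and EULAR series after Week 264 confound who remains with change within patients, and no planned analysis separates them. The rule-based exits at Week 264 and the 2020 closure establish the change of population from the documents alone.

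Its size does not follow from the documents. Under the assumed 10% to 80% continuing and a 0 to 15 point remission gap, the boundary shift is 0 to 13.5 points either way.

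Two stronger readings are tempting and unsupported. One is that the curves will show a spurious loss of efficacy: neither direction nor presence of a gap can be derived. The other is that stayers are known to differ by parent study. Country follows from the exit rule and enrolment period from the date arithmetic. Parent study is an inference, since the documents do not give enrolment dates by study. This is an inexpensive improvement, not a defect that invalidates the plan.

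**What to change.** Keep the planned by-visit tables, including the visits after Week 264, but mark Week 264 on tables and figures as the end of the full-population trend. There is no need to delete the later visits that Amendment 9 provides for.

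Add a table and figure for DAS28-CRP, DAS28 remission and EULAR response, restricted to patients with an assessment after Week 264. Show that same cohort at baseline, Week 0, every visit to Week 264 and the later visits (for EULAR response, from the first visit at which it is defined), with n at each visit.

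State in a footnote that this cohort continues to shrink with later launches and the 2020 closure. The display removes the artificial step at the boundary, but it does not hold composition constant out to Week 516.

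The cost is some additional descriptive output across these endpoints. No new data are needed.

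Suggested wording for SAP 2.4.5: *For DAS28-CRP, DAS28 remission and EULAR response, an additional by-visit summary will be restricted to patients with at least one assessment after Week 264 and will present this cohort from baseline onward with the number of patients at each visit.*

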#### **2.4.5.1 Multiplicity issues**

Not applicable.

#### **2.4.6 Analyses of pharmacokinetic and pharmacodynamic variables**

The baseline value for PK and PD variables is the original baseline from the previous studies. The value at Week 0 is the last non-missing measurement in data collected at scheduled visits: visit1, visit2, and/or visit1/2 in LTS11210 or EOT visit of previous studies prior to first IMP in LTS11210 study design.

No PK values at baseline and Week 0 for patients with placebo treatment in EFC10832 and patients with active control (Tocilizumab) treatment in SFY13370. No ADA sample values at baseline and Week 0 for patients with active control (Tocilizumab) treatment in SFY13370.

##### ***Pharmacokinetic variables***

All the PK analyses will be performed using the PK population.

Serum samples will be analyzed for functional SAR153191 concentrations using validated enzyme-linked immunosorbent assay (ELISA) methods with a targeted lower limit of quantitation (LLQ) of 0.294 mg/L (*REGN88-AV-07026-SA-01V1*) or 0.3125 mg/L (*REGN88-AV-13131-VA-01V1*). Serum concentrations of functional sarilumab will be summarized using arithmetic and geometric means, standard deviation (SD), standard error of the mean (SEM), coefficient of variation (CV%), minimum, median and maximum by actual dose and visit. Concentrations below LLOQ were replaced by LLOQ/2.

After the completion of EFC11072 (Mobility) Part B study, the Sponsor made the decision to discontinue measurement of bound sarilumab concentration from ongoing studies globally. Serum concentrations of bound sarilumab (serum sarilumab-sIL-6R $\alpha$  complex) will not be summarized in this study.

##### ***Pharmacodynamics variables***

Serum concentrations of IL-6 will be summarized using descriptive statistics (including number, arithmetic and geometric means, standard deviation, standard error of the mean (SEM), coefficient of variation (CV%), minimum, median and maximum) by actual dose received at each visit.

#### **2.4.7 Analyses of quality of life/health economics variables**

The summary statistics will be provided for the 8 dimensions of SF-36 and the 2 summary measures of physical and mental health (raw value and change from baseline) at each visit or study assessment (baseline, endpoint) by treatment group. Summary statistics will also be produced for WPAI questionnaires, FACIT-Fatigue, WPS-RA and the sleep questionnaire scales.

